17.5.2. Exploratory Analyses: Impact of Events on Quality-Adjusted Life Expectancy

One of the secondary goals of this study is to better understand the relative impact of outcome events on overall subject health. For these analyses, the longitudinal growth curve models to estimate quality of life over time for the two treatment groups will be used. Similar to the approach described above, these analyses will incorporate all available QoL scores including those for subjects who die, withdraw from the study, or are lost to follow-up. Variables included in the longitudinal models for each outcome will include treatment (according to intention to treat), follow-up time (using linear, quadratic, and cubic terms), and interactions between treatment and each time term. In addition, a broad range of baseline sociodemographic and clinical characteristics will be included. Finally, these models will include terms for each outcome variable of interest including myocardial infarction, stroke, and the occurrence of one or more repeat revascularization procedures (as time-dependent covariates). The interpretation of these analyses will be focused on the beta coefficients, which will indicate the independent impact of each outcome event on the various health status domains (including utility weights) for subjects undergoing revascularization for left main disease.

17.5.4. Cost-Effectiveness Analyses

Cost effectiveness will be expressed in terms of the incremental cost-effectiveness ratio, comparing the more effective treatment (Treatment A) to the less effective treatment (Treatment B). The cost-effectiveness ratio is calculated as:

Mean Cost (Treatment A) – Mean Cost (Treatment B) Effectiveness (A) – Effectiveness (B)

where effectiveness is measured either in terms of quality-adjusted life years, life-years, or in terms of the proportion of subjects experiencing a major adverse event (death, MI, stroke +/- repeat revascularization). For the purposes of these analyses, all costs will be expressed in constant dollars and both future costs and quality-adjusted life years will be discounted at 3%/year, consistent with current guidelines. ¹⁷² For each analysis, a cost-effectiveness acceptability curve to relate any specific cost-effectiveness threshold to the probability of treatment A being cost-effective at that threshold will be constructed.

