To date, the only available data regarding the cost-effectiveness of PCI for left main disease are derived from the 1-year follow-up of the SYNTAX trial (Cohen DJ, ACC Scientific Sessions 2009). For the overall population of subjects with either 3-vessel or left main disease, initial revascularization costs were ~\$6000/subject greater with CABG than with PCI. Over the subsequent 12 months, repeat revascularization was significantly more common with initial PCI such that follow-up costs were ~\$2500/subject greater with PCI. Thus, at 12 months, total medical care costs remained greater with CABG, by approximately \$3500/subject. Because there were no differences in overall survival yet short-term quality of life was better with PCI, quality adjusted life expectancy was also slightly greater with PCI at this early timepoint. Consequently, PCI with DES was an economically dominant strategy at this relatively early timepoint. Results were even more favorable for the subgroup of subjects (n=701) with left main disease. Among this subset, 1-year costs were \$6300/subject higher with CABG and qualityadjusted life expectancy also favored PCI (by 0.03 QALYs) rendering PCI a highly dominant strategy at this relatively early timepoint. Although these results suggest that PCI could be a highly attractive strategy from both a clinical and economic perspective for subjects undergoing revascularization for left main CAD, longer term follow-up and additional confirmatory data will be required to determine the durability and reproducibility of these findings.

2.6. Justification for a Contemporary Large-Scale Trial Comparing PCI and CABG for LMCA Disease

The SYNTAX trial is the largest contemporary trial of DES vs. CABG in patients with complex coronary artery disease, and with a primary endpoint of death, MI, stroke or repeat revascularization at one year, confirmed the superiority of CABG compared to PES. As a result the SYNTAX investigators concluded that "CABG remains the standard of care for patients with three-vessel or left main coronary artery disease, since the use of CABG, as compared with PCI, resulted in lower rates of the combined end point of major adverse cardiac or cerebrovascular events at one year."⁷ However, SYNTAX was not powered to examine the outcomes of patients only with left main coronary artery disease (with or without other diseased coronary vessels).

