7.2.10. QoL Questionnaire

Subjects in the QoL substudy of the randomized trial should complete the Quality of Life (QoL) questionnaires after being determined to be eligible for randomized study participation but prior to randomization. Subjects who have intermediate lesions who require an additional angiogram to determine eligibility should complete the QoL questionnaire prior to the additional angiogram in case the randomization assignment is to PCI and the angiogram procedure continues into the PCI treatment without leaving the catheterization laboratory.

Disease-specific QoL will be assessed using the Seattle Angina Questionnaire (SAQ) and the London School of Hygiene Dyspnea Questionnaire in 1800 selected patients. Mental health and depression will be assessed using the Patient Health Questionnaire-9 (PHQ-9). Generic health status will be assessed using the Medical Outcomes Study 12-item Short Form (SF-12), and health utilities will be assessed using the EuroQoL (EQ-5D) with U.S.-specific weights. These measures will be assessed using standardized, written questionnaires at baseline (prior to randomization), 1 month, 12 months, 3 years, and 5 years. Questionnaires will be presented in each subject's native language using culturally-validated translations. When an appropriate translation does not exist for the instrument, it will be omitted from the specific country but the remainder of the questionnaires will still be administered. Data entry for each questionnaire into the study database will be the responsibility of an appropriate contract research organization (CRO).

See Section 17, Appendix B. for details regarding Quality of Life and U.S. Health Economics Sub-Studies.

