9.3.2. Quality of Life

HRQoL and functional status will be assessed using a combination of generic and diseasespecific measures selected to cover a broad range of health domains that may be affected by coronary artery disease, its treatment, and its complications in about 1800 patients. Diseasespecific QoL will be assessed using the Seattle Angina Questionnaire (SAQ)^{77, 78} and the London School of Hygiene Dyspnea Questionnaire.^{79, 80} Mental health and depression will be assessed using the Patient Health Questionnaire-9 (PHQ-9).⁸¹ Generic health status will be assessed using the Medical Outcomes Study 12-item Short Form (SF-12),⁸² and health utilities will be assessed using the EuroQoL (EQ-5D) with U.S.-specific weights.^{83, 84} Further details regarding the rationale for selection of these instruments and specific analytic approaches are detailed in Section 17. These measures will be assessed using standardized, written questionnaires at baseline (prior to randomization), 1 month, 12 months, 3 years, and 5 years.

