17.2. Subject Population

The population for the quality of life and cost-effectiveness sub-studies will consist of 1800 subjects. The primary analyses will be conducted on an intention-to-treat (ITT) basis. In particular, any subjects who die prior to receiving their initial revascularization procedure will be retained in the ITT analyses and considered as part of their randomization group. Secondary analyses will be performed based on the per-protocol population (i.e., sub-study subjects who receive their assigned treatment) and a treatment-received population (sub-study subjects based on the initial revascularization procedure performed).

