There are a number of potential techniques for measurement of subject-specific, populationbased utility weights within the EXCEL trial. These include the Health Utilities Index (HUI),¹⁵⁹ the Quality of Well-Being Scale (QWB),¹⁶⁰ the EuroQol (EQ-5D),⁸³ and recently published algorithms that allow mapping of the SF-36 or SF-12 to health state utilities.^{161,162} Although each of these approaches has intrinsic advantages (and disadvantages), the preferred utility instrument for the EXCEL trial is the EQ-5D. The EQ-5D is a multiattribute health status classification system with an empirically-derived preference based scoring system based on analysis of time trade-off utilities for selected health states among 2997 randomly-selected members of the adult population of the U.K.¹⁶³Recently, analogous preference-weights have been developed for U.S. population utilities.⁸⁴ Although the EQ-5D was not specifically developed for use in subjects with coronary artery disease, it offers several specific advantages for this trial. First, it is based on a health state classification system that includes five specific domains of health: mobility, self-care, usual activities, pain/discomfort, and anxiety/depression. By incorporating many of the domains that are likely to be affected by coronary artery disease and its complications, such as pain, physical limitations, and role limitations, the EQ-5D should capture important differences in health within the study population. Second, the EQ-5D may be administered by either a five item written questionnaire or telephone interview and thus should add little burden to the overall data collection task. By comparison, both the HUI and the QWB questionnaires are substantially longer and, in previous experience, are often too burdensome for chronically-ill subjects. Finally, considerable practical experience with the EQ-5D exists as it has been used successfully as the principal utility measure in the Benestent II Trial $(n=823)^{164}$ and the PAMI Stent trial (n=900), ¹⁶⁵ and most recently in the SYNTAX trial.

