17.5. Analytic Plan

17.5.1. Quality of Life Endpoints

Since quality of life is a multidimensional construct for which different subjects may have different individual preferences, no specific scale will be considered as the "primary" QoL endpoint of the EXCEL trial. Rather, the goal of the study will be to describe any differences in the various quality of life scales over the time-frame of the trial. To limit any "false positive" results due to the large number of scales and timepoints evaluated, all QoL analyses will be performed using a p-value of <0.01 as an indicator of statistical significance.

For each of the quality of life measures in this study, data analysis will proceed in two stages. First, a simple descriptive and comparative analyses of cross-sectional data by intention-to-treat will be performed. For these cross-sectional analyses, comparisons will be performed at each follow-up timepoint using analysis of covariance to adjust for any baseline differences, including baseline score, between the treatment groups. Second, in order to account for missing data, longitudinal random coefficient growth curve models will be used to examine the effect of CABG versus PCI over time on each health status/QoL outcome. These models readily accommodate linear and nonlinear changes over time, as well as missing data patterns commonly seen in longitudinal studies. These analyses will incorporate all available QoL scores including those for subjects who die, withdraw from the study, or are lost to follow-up. Variables included in the longitudinal models for each outcome will include treatment (according to intention to treat), follow-up time (using linear, quadratic, and cubic terms), and interactions between treatment and each time term. In addition, these analyses will adjust for any baseline sociodemographic and clinical factors that differ between the two groups.

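### The documents specify no baseline EQ-5D adjustment for incremental QALYs, which loses precision and leaves chance baseline imbalance in the realised difference

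*Protocol*

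**What the plan says.** Section 17.5.4 of the protocol (Appendix B) divides the difference in mean cost by the difference in effectiveness between treatments A and B, "where effectiveness is measured either in terms of quality-adjusted life years, life-years, or in terms of the proportion of subjects" with a major adverse event. It adds 3% annual discounting and an acceptability curve. It names no covariate.

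The utility behind the QALY is settled in section 17.3.4: "the preferred utility instrument for the EXCEL trial is the EQ-5D". On timing, section 9.3.2 says: "These measures will be assessed using standardized, written questionnaires at baseline (prior to randomization), 1 month, 12 months, 3 years, and 5 years". On size, section 17.2 says: "The population for the quality of life and cost-effectiveness sub-studies will consist of 1800 subjects". Section 7.2.10 makes one exception: "When an appropriate translation does not exist for the instrument, it will be omitted from the specific country".

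For the quality-of-life scores, section 17.5.1 compares the arms at each follow-up visit "using analysis of covariance to adjust for any baseline differences, including baseline score". EQ-5D is one of those measures, so it is baseline-adjusted as a score.

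The other economic sections do not carry this over to QALYs. Section 9.3.3 describes the cost-effectiveness analysis without it. Section 17.5.3 specifies bootstrapping for cost endpoints. Section 17.5.5 projects lifetime outcomes. Section 17.5.6 uses net benefit regression only to look for differences between countries. SAP section 2.3.4 defers quality-of-life and economic analyses to a document that is not supplied, and SAP Appendix A gives only means and standard deviations of the scores.

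**The concern.** The same utilities are baseline-adjusted when compared as scores at a visit, but no adjustment is specified once they are accumulated into QALYs, the quantity on which the cost-effectiveness conclusion rests.

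Later utility is normally correlated with baseline utility. If one arm starts slightly better by chance, part of that advantage persists and accrues as QALYs in each year of follow-up. An unadjusted comparison leaves it in the estimate. It also leaves predictable between-patient variation in the error term, so the interval and the acceptability curve are wider than they need be.

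This matters more when the expected difference is small. The only figure of that kind in the protocol is 0.03 QALYs in favour of PCI at 1 year, in the left main subgroup of the SYNTAX trial (section 2.5).

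**Working it through.** There is no plan figure to reproduce: the documents give no SD, correlation, precision or power for the QALY difference.

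**Inputs from the documents**
- 1800 sub-study patients (17.2) allocated 1:1 (4.1), so about 900 per arm.
- EQ-5D at baseline, 1 month, 12 months, 3 years and 5 years (9.3.2).
- 0.03 QALYs at 1 year, for scale (2.5).

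**Assumptions, not in the documents**
- Utility SD 0.15 to 0.25, the same at each visit.
- Correlation rho of 0.3 to 0.6.
- Simple 1:1 allocation, no deaths, no missing data, no discounting.

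**Step 1. Chance imbalance at baseline.** SE of the baseline difference = SD × √(2/900).
- SD 0.15: 0.0071
- SD 0.20: 0.0094
- SD 0.25: 0.0118

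**Step 2. Carry-over into QALYs.** With rho the correlation of baseline with later utility, a one-SE imbalance shifts the difference over T years by about T × rho × SE.

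| Case | 3 years | 1 year | 1-year shift as share of 0.03 |
|---|---|---|---|
| SD 0.15, rho 0.3 | 3 × 0.3 × 0.0071 = 0.006 | 0.002 | 7% |
| SD 0.20, rho 0.5 | 3 × 0.5 × 0.0094 = 0.014 | 0.005 | 16% |
| SD 0.25, rho 0.6 | 3 × 0.6 × 0.0118 = 0.021 | 0.007 | 24% |

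The share is given only at 1 year, because 0.03 is a 1-year figure and the documents give no expected 3-year difference.

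**Step 3. Precision.** If rho is instead the correlation between baseline utility and the QALY itself, adjusted SE = unadjusted SE × √(1 − rho²).
- rho 0.3: √0.91 = 0.954, a 5% reduction
- rho 0.4: √0.84 = 0.917, 8%
- rho 0.5: √0.75 = 0.866, 13%
- rho 0.6: √0.64 = 0.800, 20%

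**Step 4. Check with QALYs built from the visits.** The documents do not say how QALYs are computed, so this uses area under the curve by trapezoids to 3 years. The weights on baseline, 1 month, 12 months and 3 years are 0.042, 0.500, 1.458 and 1.000. With a common correlation of 0.5 between visits, the slope of QALY on baseline is 0.042 + 0.5 × 2.958 = 1.52, close to the 1.5 used in Step 2. Averaging several visits makes the correlation of baseline with the QALY higher than that between single visits (0.61 against 0.5). At SD 0.20 the SE then falls from 0.0235 to 0.0186, or 21%; at a between-visit correlation of 0.3 the fall is 9%. A simulation of 3,000 trials at SD 0.20 and correlation 0.5 gave a mean error of about 0.0002 for both estimators, and an SD of the estimate of 0.0234 unadjusted and 0.0187 adjusted.

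**The case against.** The strongest reply is that the plan is silent here and has not chosen an unadjusted estimator. The formula in 17.5.4 is the generic definition of the ratio, and an adjusted increment would fit it. The introduction to Appendix B describes its content as general analytic plans, and SAP 2.3.4 points to another document. This stands as a limit on wording: a reader might infer that the sponsor has committed to a raw difference of arm means, and the text does not say so. It does not remove the point, because nothing supplied shows that the adjustment is planned.

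Other parts of the reply also stand:
- The unadjusted difference is unbiased under randomization, and its interval already allows for chance imbalance. A reader might infer a biased result; the loss is in precision and in the one realised estimate.
- Randomization is stratified by diabetes, SYNTAX score and center (9.1.9.1). That limits imbalance in utility related to those factors, so Step 1 may overstate it.
- A reader might infer lost power. No QALY test is planned or powered, and section 17.6 calls cost-effectiveness analysis descriptive.
- A reader might set the 3-year shift against 0.03 and infer that the sign could easily change. The horizons differ. At 1 year with SD 0.20 and rho 0.5, reversing 0.03 would need an imbalance of about six standard errors (0.03/0.0047).
- Baseline EQ-5D cannot be assumed for every sub-study patient, given the translation exception.

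Section 17.5.1 would reveal a baseline EQ-5D imbalance and adjust the visit-by-visit utility comparisons for it. It does not say that the adjusted values feed the QALY difference. The growth models in 17.5.2 are exploratory and aim at the effect of clinical events.

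**Conclusion.** The point holds as an available improvement in efficiency. As supplied, the documents specify no baseline EQ-5D adjustment of incremental QALYs, although the covariate is scheduled and the same adjustment is planned for the score comparisons.

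Under the stated assumptions, a one-standard-error imbalance shifts the 3-year difference by about 0.006 to 0.021 QALYs and the 1-year difference by about 0.002 to 0.007, the latter being 7 to 24% of the protocol's 1-year benchmark. Adjustment cuts the standard error by roughly 5 to 20% when correlation is measured between baseline utility and QALYs. Deaths and missing data would reduce the gain. No magnitude is claimed for the lifetime horizon.

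The point does not touch the primary endpoint or the definition of study success in SAP 2.7. It is still worth settling in advance, because section 17.6 allows the economic plan to be modified in response to trial results, and adjustment adopted after an imbalance is seen would look data-driven.

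**What to change.** In section 17.5.4, state that incremental QALYs are estimated by regressing patient-level QALYs on treatment and baseline EQ-5D utility, with medically treated diabetes and SYNTAX stratum (<23 vs ≥23) as further covariates. Center is also a stratification factor; with about 165 sites it may be handled by region or country.

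Fit this regression within each bootstrap replicate, resampling cost and QALYs together for each patient, and use the adjusted increment for the ratio and the acceptability curve. Impute scattered missing baseline EQ-5D values simply, for example by the overall mean without reference to treatment. A country without the instrument would lack follow-up EQ-5D too, so that gap affects the QALY itself under either estimator. Report the unadjusted difference as a sensitivity analysis.

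Where the lifetime model in 17.5.5 is calibrated to 3-year outcomes, calibrate it to the adjusted 3-year QALY difference. No other change to 17.5.5 is needed for this point.

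The cost is a few sentences in Appendix B and a regression step in the analysis code, with no new data. If the separate economic plan already specifies the adjustment, a cross-reference in 17.5.4 is enough.

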17.5.5. Lifetime Cost-Effectiveness

If there are important differences in irreversible clinical outcomes between the PCI and CABG groups, a life-time cost-effectiveness analysis will be performed in addition to the within-trial analysis described above. For this analysis, the data from the in-trial analysis to project life-expectancy and quality-adjusted life expectancy for each surviving subject will be used, contingent on the observed clinical outcomes during the trial. If there are differences in survival, the remaining life-expectancy for the two treatment groups will be estimated by relating the observed annual follow-up mortality to the mortality that would have been predicted based on a comparable age- and gender-matched U.S. population.¹⁷³ Quality-adjusted life expectancy will be calculated by assuming that each subjects' health status remains unchanged beyond the last observation in the trial.

On the other hand, if there are differences in other non-fatal outcomes but not survival, a statetransition (Markov) model will be developed to project lifetime costs, survival, and qualityadjusted life expectancy for each treatment group.¹⁷⁴ The model will be developed based on the observed within-trial data and calibrated to match the 3-year outcomes (in terms of aggregate costs and quality-adjusted life-expectancy) for the two treatment groups. Under this approach, standard one-way, multi-way, and probabilistic sensitivity analyses will also be performed to explore the impact of plausible variations in the assumptions on the incremental costeffectiveness ratios.

17.5.6. Evaluation of Heterogeneity by Country

Given that the primary cost-effectiveness analysis will be based on approximately 1800 patients of EXCEL trial population, a series of heterogeneity tests will be performed to identify whether it is appropriate to generalize these results to the U.S. as a whole or whether an analysis based specifically on U.S. subjects is more appropriate.¹⁷⁵Although heterogeneity in terms of costs and

clinical outcomes can be evaluated through standard statistical techniques and interaction tests, heterogeneity in cost-effectiveness results will be evaluated using a net benefit regression approach through the use of country by treatment group interaction terms. ¹⁷⁶ Because of the inherently low power of these tests, clinical outcomes, resource use, and cost and cost-effectiveness results will be stratified by country as well, in an effort to identify countries with markedly outlying clinical, economic or cost-effectiveness outcomes. If important heterogeneity is detected, results for a particular country may need to be based on the individual country data or on pooled data with other countries with comparable outcomes and resource use.

